#### ***Withdrawal of individual subjects and replacement***

Subjects can leave the study at any time for any reason if they wish to do so without any consequences. The investigator can decide to withdraw a subject from the study for urgent medical reasons. Also patients with an ovarian tumour and benign result at frozen section during surgery will be excluded from the study.

These patients will be replaced by a new study subject until 20 completed sentinel node procedures are performed.

[figure not shown]
#### ***Follow-up of subjects withdrawn from treatment***

The reasons why patients have left the study after initial inclusion will be documented in a anonymous way.

#### ***Premature termination of the study***

- When after 1 year <5 patients have been included.
- When in < 50% of patients the sentinel nodes are identified (interim analysis after 10 procedures).

**Figure 1:** location of lymph nodes

## 6. SAFETY REPORTING

### ***Section 10 WMO event***

In accordance to section 10, subsection 1, of the WMO, the investigator will inform the subjects and the reviewing accredited METC if anything occurs, on the basis of which it appears that the disadvantages of participation may be significantly greater than was foreseen in the research proposal. The study will be suspended pending further review by the accredited METC, except insofar as suspension would jeopardise the subjects' health. The investigator will take care that all subjects are kept informed.

### ***Adverse and serious adverse events***

Because both the blue dye and the radioactive tracer are injected outside the ovary, there is no risk of spread of tumour cells.

An allergic reaction can occur due to the blue dye. The clinical presentation can range from urticaria, skin rash, blue hives, erythema, hypotensive episodes to an anaphylactic shock. For breast cancer minor reactions are reported in 0.9% of the sentinel node procedures. Severe allergic reactions, requiring administration of vasopressor occurred in 4 of 5853 procedures (0.07%). Anaphylactic shock after administration of blue dye is considered a medical emergency [30]. The anaesthesiologist is informed of the use of dye during the surgery, before the start of the surgery. Adequate fluid supply and if necessary resuscitation can be given in the setting of the surgery. Epinephrine injections can be given to treat hypotension, salbutamol spray for bronchospasms [31].

All SAEs will be reported through the web portal *ToetsingOnline* to the accredited METC that approved the protocol, within 15 days after the sponsor has first knowledge of the serious adverse reactions.

SAEs that result in death or are life threatening should be reported expedited. The expedited reporting will occur not later than 7 days after the responsible investigator has first knowledge of the adverse reaction. This is for a preliminary report with another 8 days for completion of the report.

***Follow-up of adverse events***

All adverse events will be followed until they have abated, or until a stable situation has been reached. Depending on the event, follow up may require additional tests or medical procedures as indicated, and/or referral to the general physician or a medical specialist.

***Data safety Monitoring Board (DSMB)***

The principle of sentinel nodes is familiar for several malignancies, among others breast and vulvar cancer. With respect to ovarian cancer the knowledge is limited and so far only studied by injecting the tracers in the ovarian cortex with the possible risk of tumour dissemination. The method described in this protocol (injection in the ovarian ligaments) has no risk of tumour dissemination. No new medicaments or substances are tested. Both the blue dyes as well as the radioactive tracers are known substances used for detecting sentinel nodes related to other malignancies. Therefore no DSMB is involved in this feasibility study.

## **7. STATISTICAL ANALYSIS**

***Descriptive statistics***

Registered items:

- Sentinel nodes
  - o Number per patient
  - o Location(s) per patient
  - o Number(s) of sentinel nodes containing a metastasis per patient
  - o Location of sentinel nodes containing a metastasis per patient
- Non-sentinel lymph nodes removed during the subsequent staging procedure
  - o Number per patient
  - o Location(s) per patient
  - o Number(s) containing a metastasis per patient
  - o Location of non sentinel nodes containing a metastasis per patient

Based on the above registered items the median and mean number of sentinel nodes and its main locations can be determined. By combining the data of the sentinel en non-sentinel nodes, cases in which de sentinel node is false negative can be identified

***Interim analysis.***

For the surgeons there will be probably a learning curve for applying the injection and detecting the nodes, therefore initially the detecting rate of the sentinel node(s) in this pilot study should not be set to high. Nevertheless, an interim analysis will be done once we have included 10 patients in whom the sentinel node procedure could be performed. This will be done by one of the investigators. If less than 50% of the cases no sentinel node(s) could be detected the study will prematurely end.

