#### *During surgery*

Removal of lymph nodes:

- systematic lymphadenectomy / lymph node sampling

Approaches range from taking some lymph nodes only (lymph node sampling) to systematic lymphadenectomy [22]. A systematic lymphadenectomy can be seen as the golden standard. However, such a radical procedure gives more late morbidity than lymph node sampling. These include the formation of lymphocyst (up to 13.5%), nerve and vessel injury (up to 4%) and increased blood loss and operating time [26, 27].

- removal of sentinel node(s)

Through a sentinel node procedure the first node that receives primary lymphatic flow can be identified (the so called sentinel node). The pathological examination is an indication of the nodal status of the remaining nodes. If the sentinel node is negative, the patient may be spared a radical lymphadenectomy and thus the morbidity that can be caused by it [28].

The sentinel node technique has been proven effective in other cancers such as breast cancer and malignant melanoma. In the gynaecological field it has been shown to be effective in vulvar cancer. Currently sentinel node studies are done for cervix en uterine cancer. Studies done for sentinel node in ovarian cancer are very limited. One article that describes the role of sentinel lymph node sampling in gynaecological cancers, only briefly mentions ovarian cancer. The authors state that the procedure is difficult due to the often bulky mass ovarian tumours. Furthermore, with injecting in the ovary there is a possible risk of tumour dissemination [28].

*Nyberg et al.* have done a study in 16 patients with high-risk uterine cancer in which technetium and blue dye were injected in the right or left ovary [29]. They used an incubation time of 15 minutes. In this study patients were included with a high-risk uterine carcinoma because these patients obtain the same operation as patients with clinical early stage ovarian cancer: a total abdominal hysterectomy (TAH) with bilateral salpingo-oophorectomy (BSO) and a pelvic and para-aortic lymphadenectomy or lymph node sampling. In 15 out of 16 patients the sentinel node was detected. Another study used activated charcoal solution to identify ovarian lymphatics in 11 patients. The charcoal was injected in the cortex of the ovary. The charcoal was deposited in the lymph nodes of all patients [12].

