### **3. STUDY DESIGN**

Observational feasibility study to detect sentinel nodes: mapping the lymphatic drainage of the ovaries.

The study will end after 20 patients, of which at least 10 patients with ovarian cancer, are included in which the complete sentinel node procedure has been performed. The expected inclusion period is estimated to be two years. If the detection rate of the sentinel node is less than 50%, or when less 5 patients are included in a year, the study will end prematurely.

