***Sample size calculation***

Between 24 and 28 patients will be included in the study.

The sample size calculation is based on the fact that:

- with a group of 20 evaluable patients the study group is large enough to give an answer whether sentinel node(s) can be detected related to the ovarian lymphatic flow when the tracers are injected in the ovarian ligaments. For this purpose both patients with an ovarian and endometrial malignancy, planned for a staging laparotomy can and will be included.
- patients with a benign result on frozen section of the suspicious ovary will be excluded from the study because no lymph node(s) will be resected in these patients. These patients will be documented and described in the report after the study.
- based on retrospective data, in 60% of the patients with a suspicious ovary, frozen section will confirm a ovarian malignancy.
- to calculate one of the secondary endpoints (incidence of false negative sentinel lymph node) at least 10 patients with ovarian cancer should be part of the 20 evaluable patients.

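### The interim stopping rule in the statistics section is worded backwards: read literally, it ends the study when detection succeeds, contradicting two other sections of the protocol

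*Protocol*

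**What the plan says.** Three places in the protocol state a stopping rule based on detection.

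- Section 7, Interim analysis: the look takes place once the procedure could be performed in 10 patients, and "If less than 50% of the cases no sentinel node(s) could be detected the study will prematurely end". The sentences before it explain that, because surgeons face a learning curve, "initially the detecting rate of the sentinel node(s) in this pilot study should not be set to high".
- Section 5, Premature termination of the study: the study ends "When in < 50% of patients the sentinel nodes are identified (interim analysis after 10 procedures").
- Section 3, Study design: the study ends early "If the detection rate of the sentinel node is less than 50"%. No interim size or timing is given there.

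The other ground for early termination is accrual: "When after 1 year <5 patients have been included". On oversight, an investigator carries out the interim look, and Section 6 says "Therefore no DSMB is involved in this feasibility study".

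**The concern.** Sections 5 and 7 describe the same look, after 10 procedures, with the same 50% cut-off, but they apply the cut-off to opposite quantities. Section 5 applies it to patients in whom a node was found. Section 7 applies it to cases in which none was found. Fewer than half without a node means more than half with one, so the Section 7 sentence tells the investigator to stop a technique that works and to continue one that does not.

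This is the only stopping threshold that depends on the study's outcome. The protocol does not say which section prevails, and no independent board would apply or check the rule.

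If the sentence were followed as written, a working technique would end at 10 of the 20 planned procedures. The sample size section also asks that "at least 10 patients with ovarian cancer should be part of the 20 evaluable patients", for the false negative endpoint. A study stopped at 10 procedures could meet that number only if all 10 were in ovarian cancer patients.

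**Working it through.** **Inputs.** The interim size is n = 10 (Sections 5 and 7), the cut-off is 50% (Sections 3, 5 and 7) and the planned total is 20 procedures (Section 3). The 50% is a chosen cut-off with no error rates or formula behind it, so there is no figure of the protocol's own to reproduce. The protocol gives no expected detection rate for injection in the ligaments, so every true rate p below is an assumption. One value, 15/16 = 93.75%, comes from the earlier study of injection in the ovary cited in Section 1 ("In 15 out of 16 patients the sentinel node was detected").

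**Step 1: decision regions.** Let d be the number of the 10 procedures with a node detected.

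- Section 7, literal: stop if (10 − d)/10 < 0.5, so d > 5, which is d = 6 to 10.
- Section 5: stop if d/10 < 0.5, so d < 5, which is d = 0 to 4.
- At d = 5 both proportions equal 0.5, neither is below it, and both wordings continue.

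Of the 11 possible results (0 to 10), 5 + 5 = 10 give opposite decisions and one gives agreement.

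**Step 2: probability of stopping.** With d ~ Binomial(10, p), the literal wording stops with probability P(d ≥ 6) and Section 5 with probability P(d ≤ 4). The two agree only with probability P(d = 5).

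**Step 3: expected number of procedures.** If every study that continues reaches 20, this is 10 + 10 × (1 − P(stop)). For example, at p = 0.70 the literal wording gives 10 + 10 × (1 − 0.8497) = 11.5, and Section 5 gives 10 + 10 × (1 − 0.0473) = 19.5.

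| Assumed p | P(stop), Section 7 literal | P(stop), Section 5 | P(agree) | Expected procedures, literal | Expected procedures, Section 5 |
|---|---|---|---|---|---|
| 0.30 | 0.0473 | 0.8497 | 0.1029 | 19.5 | 11.5 |
| 0.50 | 0.3770 | 0.3770 | 0.2461 | 16.2 | 16.2 |
| 0.70 | 0.8497 | 0.0473 | 0.1029 | 11.5 | 19.5 |
| 0.90 | 0.9984 | 0.00015 | 0.0015 | 10.0 | 20.0 |
| 0.9375 | 0.9998 | 0.00001 | 0.0002 | 10.0 | 20.0 |

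The two stopping columns mirror each other around p = 0.50, as expected when a 50% rule is negated. The equal values at p = 0.50 do not mean that the rules agree there: they stop on different results and coincide only at d = 5.

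**The case against.** The strongest reply is that nobody would be misled. Section 5 states the rule completely and names the same interim, and Section 3 gives the same direction. The lead-in in Section 7 about a learning curve makes sense only for a minimum detection rate. Stopping a feasibility study because the technique works would defeat its primary objective. The sentence is also ungrammatical, so its literal reading is partly a reconstruction. On this view it is an editorial slip, and the probabilities describe an event that nothing in the document makes likely.

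Much of this stands. The intent is recoverable, a reader of the whole protocol would probably apply the intended rule, and the figures above measure how far apart the wordings are, not how likely a wrong decision is. The expected numbers also ignore the accrual rule, and the 93.75% belongs to a different injection site.

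It does not make the sentence right. The sentence sits under the heading where a reader looks for the interim rule, and someone with only that section holds a threshold pointing the wrong way. The ethics committee must be told of a premature end and its reasons, and receives a progress report after one year. That oversight might expose a wrong stop, but it does not correct the rule.

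**Conclusion.** The point holds. The Section 7 sentence contradicts Section 5 on the same look and Section 3 in direction, and the decisions differ at every result except 5 of 10. That conclusion needs no assumption beyond the wording. The stopping probabilities and expected procedures hold only if the sentence is applied literally. They also rest on assumed true detection rates, independent procedures and, for the expected numbers, every continuing study reaching 20.

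This is an internal inconsistency from drafting. It does not show that an inverted rule was planned, and it calls neither the 50% threshold nor the interim size into question. It should be fixed because it is a stated decision rule that is wrong as written.

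**What to change.** Replace the last sentence under Interim analysis in Section 7 with: *If sentinel node(s) are detected in fewer than 50% of the first 10 procedures (4 or fewer of 10), the study will end prematurely.* This restates the Section 5 rule, agrees in direction with Section 3, and introduces no new threshold. Since Section 3 gives no timing, a cross-reference there to Section 5 would be a useful optional addition.

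The cost is one sentence in an amendment. No patients, procedures or analyses are added.

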## **8. ETHICAL CONSIDERATIONS**

***Regulation statement***

The study will be conducted according to the principles of the Declaration of Helsinki (see for the most recent version: [www.wma.net](http://www.wma.net)) and in accordance with the Medical Research Involving Human Subjects Act (WMO).

***Recruitment and consent***

The recruitment will be done by the gynaecologic oncologists based in the Maastricht University Medical Centre. The patient will be informed by the doctor who sees her in the out patient clinic. This is not always the doctor who will do the surgery. A patient information letter will be given. The patient has at least three days to consider their decision. The patient information letter and the consent form are two separate documents. When the patient returns for a routine visit, the patient is asked whether or not she wants to participate in the study.

***Objection by minors or incapacitated subjects (if applicable)***

No minors or incapacitated subjects will be included in the study.

***Benefits and risks assessment, group relatedness***

The risk of the study are low, a small chance of 0.07-2.7% of an allergic reaction to the blue dye. The surgery will be prolonged with 20-25 minutes, which is without extra risk for the patient.

***Compensation for injury***

The sponsor/investigator has a liability insurance which is in accordance with article 7, subsection 6 of the WMO.

The sponsor has an insurance which is in accordance with the legal requirements in the Netherlands (Article 7 WMO and the Measure regarding Compulsory Insurance for Clinical Research in Humans of 23th June 2003). This insurance provides cover for damage to research subjects through injury or death caused by the study.

1. € 450.000,-- (i.e. four hundred and fifty thousand Euro) for death or injury for each subject who participates in the Research;
2. € 3.500.000,-- (i.e. three million five hundred thousand Euro) for death or injury for all subjects who participate in the Research;
3. € 5.000.000,-- (i.e. five million Euro) for the total damage incurred by the organisation for all damage disclosed by scientific research for the Sponsor as 'verrichter' in the meaning of said Act in each year of insurance coverage.

The insurance applies to the damage that becomes apparent during the study or within 4 years after the end of the study.

**9. ADMINISTRATIVE ASPECTS AND PUBLICATION*****Handling and storage of data and documents***

Each patient will be given a unique identification number (= inclusion number) to ensure the privacy of the patient. Reference to the case will only be made by means of an identification number. The acquired data will be recorded anonymously in a Microsoft Access file. This file contains the patient characteristics and surgical findings (see Study Design – data collection) and will be saved for 15 years. The members of the study group have access to the data. In a separate file, owned by the principal investigator, the patient can be identified by correlating the inclusion number with the patient's hospital number.

***Annual progress report***

The investigator will submit a summary of the progress of the trial to the accredited METC after one year. Information will be provided on the date of inclusion of the first subject,

numbers of subjects included and numbers of subjects that have completed the trial, serious adverse events/ serious adverse reactions, other problems, and amendments.

### ***End of study report***

The investigator will notify the accredited METC of the end of the study within a period of 8 weeks. The end of the study is defined as the last patient's last visit.

In case the study is ended prematurely, the investigator will notify the accredited METC, including the reasons for the premature termination.

Within one year after the end of the study, the investigator/sponsor will submit a final study report with the results of the study, including any publications/abstracts of the study, to the accredited METC.

### ***Public disclosure and publication policy***

At the end of the trial there a meeting will be planned to discuss the final data which will be published in a peer reviewed paper. At least submission of the manuscript will be done within 6 months after the study has ended.

